1. PROTOCOL SYNOPSIS

Protocol Title	A Depression and Opioid Pragmatic Trial in Pharmacogenetics (ADOPT-PGx)
US IND Number	
Grant Number	
Product/Intervention	Immediate vs. delayed pharmacogenetic testing and genotype-guided pain or depression therapy
Objectives	
Acute Pain:
 
 • To determine the effect of genotype-guided therapy on pain control and use of DEA schedule II opioids in post-surgical participants 
Chronic Pain:
 
 • To determine the effect of genotype-guided therapy on pain control in chronic pain participants 
Depression:
 
 • To determine the effect of genotype-guided selection and dosing of antidepressants on control of depression in participants with ≥ 3 months of depressive symptoms who require new or revised therapy 
All Trials:
 
 • To determine the effect of genotype-guided therapy for opioids, antidepressants, and optional additional, CPIC gene-drug pairs on overall well-being • To determine the effect of genotype-guided therapy for opioids, antidepressants, and optional additional, CPIC gene-drug pairs on healthcare utilization
Study Design	ADOPT PGx is comprised of three separate trials, Acute Pain, Chronic Pain, and Depression. Each trial is a prospective, multicenter, two arm randomized pragmatic trial. For all trials, participants will be randomized in a 1:1 ratio to immediate pharmacogenetic testing and genotype-guided therapy (Intervention arm) or 6-month delayed testing on participants receiving standard care (Control arm). In each trial, the primary outcome comparison will be between the intervention group (i.e. immediate testing) and control group (i.e. delayed testing) in the subset of participants with actionable phenotypes, within each study.
Rationale for Study Design	Pain and depression are conditions that impact substantial proportions of the US population and have challenges associated with identifying the right therapy while minimizing adverse effects or opioid addiction. There is evidence that both opioid and antidepressant prescriptions can be guided by pharmacogenetics (PGx) data based on existing guidelines from the Clinical Pharmacogenetics Implementation Consortium (CPIC). Using such an approach, a recent single site Pragmatic Clinical Trial (PCT) demonstrated that among CYP2D6 poor (PM) and intermediate

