9. MEDICARE AND MEDICAID CLAIMS DATA COLLECTION AND ANALYSIS

9.1 Rationale

The economic analyses will be conducted from the perspective of the payer with the primary goal to provide cost-effectiveness data that can inform reimbursement decisions for genotyping. Reporting metrics will include:

1. Average costs for each study arm, considering overall cost to the payer and select services directly relevant to the acute pain, chronic pain, and depression groups
2. Differences in cost utility between the intervention arm, considering overall cost to the payer and select services directly relevant to the acute pain, chronic pain, and depression groups
3. Incremental cost-effectiveness ratio (ICER), i.e., the incremental change in cost per unit improvement of effectiveness.

All metrics will be ascertained over a 6-month follow-up period with the assumption that beneficial effects of genotype-guided therapy are fully realized within this time period and that the control arm participants have not yet developed any cross-over effects from the 6-month delayed testing.

In a population of mixed payer types, collecting actual costs for all participants is not feasible. Therefore, costs will be obtained from Medicare and Medicaid claims data and imputed or cross-walked to the other payer types. Based on data in the National Inpatient Sample, 53% and 4% of knee and 59% and 4% of hip arthroplasties were reimbursed by Medicare and Medicaid, respectively. For chronic pain participants, data from the University of Florida suggest 40% and 20% are covered by Medicare and Medicaid, respectively. Thus, considering enrollment gaps, at least 60% of the study population is anticipated to have claims data, from which comprehensive cost analyses can be performed and extrapolated to the entire cohort. Major cost drivers associated with pain and depression will be ascertained from the participant using validated resource questionnaires, and verified through secondary claims data whenever possible.

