10. STATISTICAL ANALYSIS PLAN AND SAMPLE SIZE

10.1 Sample Size Determination

All trials power analyses are based on a modified intent to treat analysis, comparing the subset of intervention participants with have an actionable phenotype to the subset of control participants with an actionable phenotype. Effect sizes used to estimate power are based on prior studies of pain and depression pharmacogenetic testing and described below for each trial and shown in Table 8. Several steps were taken to generate a conservative sample size estimate. First, the power requirement was set to 90%. Second, sample sizes are adjusted for a 10% drop-out (for which UF has data from several studies that this is a good estimate). Third, slightly smaller effect sizes than what was observed in prior studies was used. Finally, sample size calculations are based on an alpha of 0.049, to allow one interim analysis with an alpha of 0.001 in each study.

Due to the study design and the delay in the control arm to obtaining the genotyping results required determine the actionable phenotype subgroup assignment, it is not feasible to directly monitor the number of randomized participants in the actionable subgroup for the enrollment stopping rule. Alternatively, the observed trial specific actionable phenotype percentages and the corresponding trial specific total enrollment targets will be used to identify when enrollment can conclude for a fully powered mITT study.

Acute Pain

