Finally, we will compare the Medicare/Medicaid beneficiaries among our trial enrollees to a larger random sample of beneficiaries in the participating states and compare demographic and key clinical characteristics to explore representativeness of our study sample, evaluate the impact of attrition and loss to follow-up and make inferences about the generalizability of our results.

Cost utility: For the cost-utility analysis, the PROMIS-43 responses will be converted into utilities using previously validated crosswalks.[41] Cost and quality adjusted life year (QALY) estimates, adjusted for clustering within site and baseline utility for QALYs, will be obtained using appropriate regression models such as generalized linear models. The analysis of maximum likelihood parameter estimates will allow us to capture differences in cost and QALYs between the intervention arm and control arm of the trial. The Incremental cost-effectiveness ratio (ICER) will be calculated from costs and QALY. A bootstrapping approach will be used to characterize sampling uncertainty and calculate confidence intervals (CI) around the ICER estimate (2.5th and 97.5th percentiles corresponding to the lower and upper bounds of the CI, respectively). This sampling uncertainty will be summarized using cost-effectiveness acceptability curves.

Details of these statistical analyses, along with other exploratory analyses will be described in the study SAP.

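### The percentile bootstrap interval on the ICER is hard to interpret unless the 6-month QALY difference is clearly away from zero; net monetary benefit from the same replicates avoids the problem

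*Combined protocol and SAP*

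**What the plan says.** Section 9.1 lists the ICER among the metrics to be reported for payers: "Incremental cost-effectiveness ratio (ICER), i.e., the incremental change in cost per unit improvement of effectiveness". The same section fixes the horizon: "All metrics will be ascertained over a 6-month follow-up period".

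Section 10.6 (Cost utility) converts PROMIS-43 responses to utilities and uses regression models to estimate "differences in cost and QALYs between the intervention arm and control arm of the trial". It continues: "The Incremental cost-effectiveness ratio (ICER) will be calculated from costs and QALY". Bootstrapping is then used to "calculate confidence intervals (CI) around the ICER estimate (2.5th and 97.5th percentiles corresponding to the lower and upper bounds of the CI, respectively". The next sentence adds: "This sampling uncertainty will be summarized using cost-effectiveness acceptability curves".

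The text has no rule for replicates whose QALY difference is zero or negative, no ordering by quadrant, and no net-benefit estimate or interval. It does not restrict the comparison to actionable phenotypes. Further detail is left to a study SAP, which Section 10.2 places in separate documents, one per trial.

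**The concern.** The ICER is a ratio of two estimated differences. Its sign does not identify the conclusion: a replicate with lower cost and more QALYs (dominant) and a replicate with higher cost and fewer QALYs (dominated) both give a negative number. Positive ratios are ambiguous in the same way, because costlier-and-better and cheaper-and-worse replicates share that side. As the QALY difference passes through zero the ratio also jumps from one extreme to the other.

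Ranking replicates by the ratio orders them by value only when they lie essentially in one quadrant. Otherwise a percentile limit is a cut through a list that mixes opposite conclusions, and a negative lower limit does not tell a payer whether the uncertainty points to savings or to harm. Section 9.1 says that these results are meant to support reimbursement decisions, so the interval is likely to be read at face value.

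**Working it through.** **1. Does the plan's own sample size reproduce?** Section 10.1 and Table 9 give 152, 134 and 271 actionable participants per arm for effect sizes of 0.375, 0.40 and 0.28, two-sided alpha 0.049 and 90% power. The two-sample t-test solution is 151.2, 133.0 and 270.4, which rounds up to those figures. Dividing by the assumed actionable shares gives the completers per arm: 152/0.18 = 844.4 (845), 134/0.30 = 446.7 (447), 271/0.40 = 677.5 (678).

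**2. How far from zero could the QALY difference be?** The documents give no QALY difference or SD, so I used the primary effect as an anchor. Let f be the fraction of the standardized primary effect that carries into 6-month QALYs (an assumption). Suppose that non-actionable participants gain nothing and that the SD is common. Then:

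- whole arms: z = f × effect size × actionable share × √(completers per arm / 2)
- actionable subset: z = f × effect size × √(actionable per arm / 2)

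Whole arms, f = 1:

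- Acute pain: 0.375 × 0.18 × √(845/2) = 1.39
- Chronic pain: 0.40 × 0.30 × √(447/2) = 1.79
- Depression: 0.28 × 0.40 × √(678/2) = 2.06

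Actionable subset, f = 1: 0.375 × √76 = 3.27; 0.40 × √67 = 3.27; 0.28 × √135.5 = 3.26.

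**3. Share of replicates with a negative QALY difference**, Φ(−z), when the estimate equals its expected value:

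| | Acute pain | Chronic pain | Depression |
|---|---|---|---|
| Whole arms, f = 1 | 8.3% | 3.6% | 2.0% |
| Whole arms, f = 0.5 | 24% | 18% | 15% |
| Actionable subset, f = 1 | 0.05% | 0.05% | 0.06% |
| Actionable subset, f = 0.5 | 5% | 5% | 5% |

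The estimate will itself vary. With whole arms and f = 1, the chance that the 95% interval for the QALY difference includes zero, Φ(1.96 − z) − Φ(−1.96 − z), is 72%, 57% and 46%.

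Table 9's ranges for the actionable share, with the matching completer counts, change the f = 1 whole-arm figures moderately. Acute pain at 15% and 24%: z = 1.27 and 1.60 (10% and 5% below zero). Chronic pain at 24% and 33%: 1.60 and 1.88 (5% and 3%). Depression at 60%: 2.53 (0.6%).

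**4. What this does to the interval (illustration only).** I drew 400,000 bivariate normal replicates with assumed standard errors of $300 and 0.005 QALY and zero correlation. The quadrant shares depend only on the two z values and the correlation; the dollar limits also depend on the assumed standard errors. A positive cost z means that the intervention costs more.

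| QALY z | Cost z | ICER percentile limits | Dominant | Dominated |
|---|---|---|---|---|
| 1 | 1 | −$625,000 to +$719,000 | 13% | 13% |
| 1 | 3 | −$1.64 million to +$1.85 million | 0.1% | 15.9% |
| 4 | 3 | $14,850 to $103,918 | 0.1% | under 0.1% |

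In the first row the negative side is an even mix of opposite conclusions. In the second it consists almost wholly of dominated replicates, so the worst outcomes sort below the favourable ones. In the third the interval is readable.

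**5. Net monetary benefit.** This is λ × QALY difference − cost difference, which is linear in both and keeps the order. At an assumed λ of $100,000 per QALY, the first row gives a point value of 100,000 × 0.005 − 300 = $200 and a 95% interval of −$938 to $1,340. In 4,000 simulated trials of 2,000 replicates for each scenario tried, coverage was 94.5% to 95.9% for net benefit and 88% to 98% for the ratio interval.

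**The case against.** The strongest reply has four parts.

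- **The trigger is assumed.** No QALY or cost difference or standard error is given, and the carry-over fraction is not in the documents. Adjustment for baseline utility, which Section 10.6 plans, would also improve precision by an amount that cannot be computed here. This stands: the problem is conditional, and every dollar figure above is illustrative. But full carry-over is a generous case, since the acute and chronic pain and depression endpoints are read at 10 days or 3 months and the QALYs run to 6 months, and even that case leaves z near or below 2 at the planned actionable shares.
- **The population could be narrowed.** In the actionable subset with full carry-over the issue all but vanishes. True, but Section 10.6 refers to the trial arms without that restriction.
- **Much of the remedy is planned.** The acceptability curve is the probability of positive net benefit at each threshold, and cost and QALY differences will be modelled. This also stands. It does not change the interval that would still be reported, and no net-benefit estimate or interval is planned.
- **Details are deferred to the SAP.** The SAPs may handle quadrants. The percentile rule is nevertheless already stated in Section 10.6.

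A reader might infer that the ICER interval is meaningless in general. The documents do not support that. When nearly all replicates lie in one quadrant the limits are ordered and usable, and simulated coverage was not far from nominal in most scenarios. The difficulty is one of interpretation when replicates span quadrants.

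**Conclusion.** The concern holds conditionally. A percentile interval on the ICER cannot be read as a range from good to bad value if the 6-month QALY difference is not clearly away from zero. On the plan's whole-arm inputs that is plausible: at most about 1.4, 1.8 and 2.1 standard errors at the planned actionable shares, with 8%, 4% and 2% of replicates below zero, rising to 24%, 18% and 15% at half carry-over. It is negligible at about 3.3 standard errors, the actionable subset with full carry-over.

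These figures assume that the primary effect size is a fair anchor for QALYs, that non-actionable participants gain nothing, and that the SD is common; the effect of baseline and site adjustment is not included. A reader might also infer that the trial's conclusions are at risk. They are not: the Synopsis calls the cost-effectiveness work exploratory, and no primary or listed secondary endpoint depends on it. This is a low-cost improvement.

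**What to change.** In the SAP, keep the bootstrap and change what is reported from it:

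- incremental cost, incremental QALYs and incremental net monetary benefit, each with a 95% interval, the last over a stated range of willingness-to-pay values;
- the cost-effectiveness plane with the share of replicates in each quadrant, beside the acceptability curve already planned;
- the ICER as a point estimate, with an interval only when nearly all replicates have a QALY difference of the same sign and lie in one quadrant, with the cut-off for nearly all set in advance.

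It would also help to state whether the cost-utility comparison uses whole arms or the actionable subset, since the size of the problem turns on that.

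The cost is a few lines of SAP text; no new data or computation is needed. The small downside is that willingness-to-pay values must be stated in advance.

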10.7 Interim Analyses

A single specified interim analysis is planned for each trial. To account for repeated significance testing of the accumulating data, the group sequential method of Lan and DeMets will be used as a guide for

interpreting this interim analysis. Monitoring boundaries for the primary endpoint will be based on a two-sided symmetric O'Brien-Fleming type spending function with an overall two-sided significance level of $\alpha=0.05$. The O'Brien-Fleming approach requires large critical values early in the study but relaxes (i.e., decreases) the critical value as the trial progresses.

Acute Pain

The interim analysis of the acute pain primary endpoint will compare SIA scores at 10 days post-surgery among participants with *CYP2D6* IM or PM phenotypes in the Control arm to participants with *CYP2D6* IM or PM phenotypes in the intervention arm.

Chronic Pain

The interim analysis of the chronic pain primary endpoint, pain control at 3 months post return of PGx testing result to providers, will be compared between the participants with *CYP2D6* IM or PM phenotypes in the Control arm and the participants with *CYP2D6* IM or PM phenotypes in the intervention arm.

Depression

The interim analysis of the depression primary endpoint, depression control at 3 months post return of PGx testing result to providers, will compare the participants with *CYP2D6* PM/UM or *CYP2C19* PM, RM and UM phenotypes in the Control arm to the participants with *CYP2D6* PM/UM or *CYP2C19* PM/RM/UM phenotypes in the intervention arm.

The primary analysis is a modified intent to treat design and the analytical subgroup is defined by the results of the PGx testing. Because the drug metabolizer phenotypes for participants in the Control arm is determined around the time of the 6-month follow up assessments for all trials (Acute Pain, Chronic Pain, and Depression), only participants that have completed their 6-month assessments will be included in the interim analysis. To account for the delays in receiving genetic testing results, the interim analysis will be targeted to occur when approximately 50% of the participants have completed their 6-month assessments. If the interim analysis does not propose stopping for efficacy (p-value <0.0003 and the intervention has the larger reduction in the primary endpoints), then the conditional power to detect a significant result at the end of the trial will be estimated. The conditional power will be presented to the DSMB to facilitate discussion of whether the trial should be stopped for futility.

